#### 3.1.4 Study methods

Two study days will be selected, and all diarrhoeal stool samples received on that day by the participating site in the study will be sent (regardless of test requested) to the European Coordinating Laboratory (Leeds), where samples will be tested for CDI using the recommended 'optimal' testing methodology (GDH/Toxin (Techlab, US) testing on the DS2, as per ESCMID guidelines), reference methods (cell-cytotoxicity neutralisation assay and cytotoxigenic culture) and a novel, Single-molecule Array (SiMoA) immunoassay platform for C. *difficile* toxins A and B. Samples will also be tested for other potential gastrointestinal pathogens (using the bioFire Film array molecular method), to investigate either co-infections or alternative cause of diarrhoea (where *C. difficile* negative). Results will be compared to those from the submitting hospital/laboratory, including if the sample was even tested. The SiMoA test will be carried out at bioMerieux (France), a COMBACTE-CDI partner, as the novel technology is currently not available elsewhere. A small portion of selected samples will be sent to BioMerieux for this purpose. They will only be labelled with the study number.

All data held by the study team will be pseudoanonymised to a study number. Only the original submitting laboratory will hold the code to link back to the patient. All samples will be sent for processing under the study number only.

All of the residual diagnostic stool samples will be processed in the laboratory facilities at the Healthcare Associated Infection Research Group (HCAI) at the University of Leeds. The HCAI laboratory is also the *Clostridium difficile* reference laboratory for the UK and has >20 years of experience in handling stool specimens and bacterial isolates derived from the samples. The laboratory follows all relevant regulatory processes for the UK, and all staff are fully trained in the relevant health and safety procedures. All work is risk-assessed for hazards (microbiological, chemical, and procedural) before commencement. Samples are handled in a class II Microbiological safety cabinet to protect the researcher.

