### **5.0 Reporting**

This is strictly an observational (surveillance) study. Results of additional testing will not be reported back to participating laboratories. The study is therefore 'non-interventional' as the participant samples will be processed as per local policy at each hospital and those results acted upon; i.e. additional COMBACTE-CDI study results will NOT be available for patient management.

Study reports and conclusions based on analysis of data at a national and European level will be prepared by the lead investigator for each objective.

A full study report will be presented at the end of each objective. Results will be submitted for presentations at scientific meetings followed by preparation of manuscript and publication whenever applicable. Authorship will be led by the lead investigator for each objective (see consortium agreement).

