#### 2. Data source

Retrospective case note data is collected on paper case report forms (CRFs) before upload onto an electronic data management system by the European coordinator.

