## 2.1 Selection of case and controls (total possible to be recruited)

		Location	of participant a sample	at time of
Diagnostic categories:		Hospital	Community	TOTAL
CDI positive cases	1. CCNA positive	83	20	103
	2. CCNA negative/Simoa positive	49	22	71
	3. CCNA and Simoa negative but CTC positive or bioFire pos	24	15	39
CDI negative controls	4. Negative control *	365	147	512
Total number selected for case/control study 521 204		725		

Table1. The total number of samples selected for the case/control study (n=725). The table shows the number of CDI positive cases according to the indicated diagnostic categories (1-3, n=213) and by location of participant (Hospital n=156, Community n=57). Negative controls (4, n=512) were selected at a rate of 1:3 from matching participating sites (one case to three controls). As some participating sites had less than 3 controls per case, average rate was of 1:2.4 (one case to 2.4 controls) (\*).

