#### 6.2. Key variables

The following is a partial list of variables that will be collected, measured and included as potential risk factors of the analysis.

- Demographic information including age, gender, etc.

- Laboratory testing for other enteric pathogens

- Medical conditions as independent variables and as a variable based on the Charleson comorbidity index (medical conditions included are listed in appendix 1)

- Medication used including antibiotics, proton pump inhibitors, drugs affecting the gastrointestinal tract, systemic steroids or immunosuppressive drugs

- Medical procedures including acute or elective surgery and GI interventions

A detailed list of the variables and definition of the variables is attached as appendix 1.

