## 7. Statistical methodology and statistical analysis

#### 7.1 Descriptive analysis

Distribution of demographic, concomitant pathogens, medical conditions, medical procedures, and medication used will be tabulated by case and controls. The analysis will also be stratified by age group (<18, 18-49 years, 50+ 50-64 years, 65 +, 65--84 years, and 85 + years).

Where data are continuous variables, means and standard deviations will be presented; where these data have a highly skewed distribution, medians, 25th and 75th percentiles will be presented. Where data are categorical variables, the number and percentage of participants within each category will be presented. The percentage of missing values will be reported for each variable (continuous or categorical).

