2.7	Did the patient receive any supportive measures/domestic help by friends or relatives during the presence of CDI?	Binary	Univariate/multivariate	Patient admission when the sample was taken

2.7.1	If yes, how many hours per day?	Continuous	Univariate/multivariate	Patient admission when the sample
				was taken
2.8	Did the patient receive any supportive measures/domestic help by professionals during the presence of CDI?	Binary	Univariate/multivariate	Patient admission when the sample was taken
2.8.1	If yes, how many hours per day?	Continuous	Univariate/multivariate	Patient admission when the sample was taken
2.9	Were any CDI related purchases necessary?	Binary	Univariate/multivariate	Patient admission when the sample was taken
2.9.1	If yes, please describe below	Categorical	Univariate/multivariate	Patient admission when the sample was taken
3. Laborat	ory Testing	1	1	
3.1	Did the patient have any test for other enteric pathogens up to 7 days before or up to 7 days after the EUCLID sample was taken	Binary	Univariate/multivariate	Patient admission when the sample was taken
3.1.1	If yes please indicate test results	Categorical	Univariate/multivariate	Patient admission when the sample was taken
3.2	What was the local policy for repeat testing of patients with CDI (at the time of the sample)	Binary (repeat or not repeat)	Univariate/multivariate	Patient admission when the sample was taken
4. CDI Test	ting	ſ	ſ	
4.1	Was the patient tested for CDI due to diarrhoea in the 6 months before the index sample	Binary	Univariate	Up to 6 months previous to the sample
4.1.1	If yes, date of sample and result of tests	Number of days between sample and	Univariate	Up to 6 months previous to the sample

		test is		
		Continuous		
		Decult of		
		Result of		
		Catagorical		
12	Did the nationt	Rinary	Univariato	Up to 6 months
4.2	have a diarrhoea	binary	Univariate	after the sample
	enisode in the 6			arter the sumple
	months following			
	the index sample			
4.3	Was the patient	Binary	Univariate	Up to 6 months
	tested for CDI in the	,		after the sample
	6 months following			
	the index sample			
4.3.1	If yes, date of	Number of	Univariate	Up to 6 months
	sample and result	days		after the sample
	of tests	between		
		sample and		
		test is		
		Continuous		
		Result of		
		test is		
		Categorical		
4.4	Was the Clostridium	Binary	Univariate	Patient admission
	difficile sent for	,		when the sample
	ribotyping?			was taken
4.5	Was the severity of	Binary	Univariate	Patient admission

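### The case/control SAP measures other enteric pathogens only through local testing and lets being tested compete as a CDI risk factor, although a uniform central panel is planned

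*SAP*

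**What the plan says.** SAP section 2 takes the data from case notes recorded on CRFs, and section 2.3 points to Appendix 1 for the complete variable list. Under protocol 3.2.6 and 3.3.6 the site's own clinical team fills in the CRF.

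Appendix 1 item 3.1 asks "Did the patient have any test for other enteric pathogens up to 7 days before or up to 7 days after" the sample. Item 3.1.1 follows: "If yes please indicate test results". The first is binary and the second categorical, and both are marked for univariate and multivariate analysis.

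- SAP 6.2 lists "Laboratory testing for other enteric pathogens" among the potential risk factors.
- SAP 7.1 states: "Distribution of demographic, concomitant pathogens, medical conditions, medical procedures, and medication used will be tabulated by case and controls". It names no source for the pathogen data.
- SAP 7.2 takes its variables from Appendix 1. SAP 7.3 offers all of them to an unconditional logistic model built by forward selection, and the order of entry is used to rank risk factors.

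A central measurement is also planned. Protocol 3.1.4 says of the coordinating laboratory: "Samples will also be tested for other potential gastrointestinal pathogens (using the bioFire Film array molecular method", in order to look for co-infection or another cause of the diarrhoea. Protocol 3.1.7 compares those results by country and by sample source. Class 3 in SAP Table 1 already draws on the panel: "CCNA and Simoa negative but CTC positive or bioFire pos". Protocol 5.0 adds: "Results of additional testing will not be reported back to participating laboratories".

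**The concern.** Central results do not go back to the sites, so items 3.1 and 3.1.1 can hold only what was requested and found locally. Item 3.1 records a decision about care, yet forward selection may rank it beside antibiotics or surgery as a risk factor for CDI. Item 3.1.1 exists only for patients whom someone chose to test.

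That choice can depend on local policy, on setting, and on whether CDI was suspected or had already been found. Uneven local testing is part of the study's premise: its primary outcome is missed CDI, including samples never tested. If cases and controls are tested at different rates, item 3.1 will show an association that says nothing about the cause of CDI, and the pathogen comparison may be distorted as well. A panel run in the same way on every sample avoids this, but the SAP does not bring its results for other pathogens into the case/control comparison.

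**Working it through.** **Case/control set.** From SAP Table 1, cases = 103 + 71 + 39 = 213 and controls = 512. The ratio is 512/213 = 2.40, which matches the stated 1:2.4.

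**Assumptions.** The documents give no local testing rates and no pathogen prevalence. All rates below are assumed. OR = [p1/(1 − p1)] / [p0/(1 − p0)], with cases as group 1.

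**1. Item 3.1, tested or not.** This needs no coding assumption.
- 50% v 60% tested: (0.50/0.50)/(0.60/0.40) = 0.67. A two-sided 5% test of two proportions with 213 v 512 patients is significant in about 70% of studies.
- 40% v 60% tested: (0.40/0.60)/(0.60/0.40) = 0.44, significant in over 99%.
- Equal testing: OR 1.00.

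**2. Item 3.1.1, pathogen found, with untested patients counted as negative.** Recorded prevalence = true prevalence × fraction tested. Take 10% true prevalence in both groups, so that the true OR is 1.0.
- 60% v 80% tested: 6% v 8%, OR = (0.06/0.94)/(0.08/0.92) = 0.73.
- 50% v 80% tested: 5% v 8%, OR = (0.05/0.95)/(0.08/0.92) = 0.61.
- 80% v 60% tested: 8% v 6%, OR = (0.08/0.92)/(0.06/0.94) = 1.36.

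**3. Item 3.1.1 among tested patients only.** With the same inputs, and testing unrelated to pathogen status, the comparison is 10% v 10% and the OR is 1.0 at every testing rate. Bias then needs testing to depend on pathogen status differently in cases and controls. That cannot be sized from the documents.

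The SAP does not choose between steps 2 and 3. Section 5 has unknown data entered as unavailable and excludes patients with a missing outcome, but it does not say how an untested patient is coded for item 3.1.1 or handled in the regression.

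**4. Does same-site selection remove the difference?** Suppose half the cases are at sites that test 80% of patients and half at sites that test 30%, with identical testing of cases and controls within each site. Let the control ratios be 3 and 1.8, which average 2.4.
- Cases tested: 0.5 × 0.80 + 0.5 × 0.30 = 55%.
- Controls tested: (1.5 × 0.80 + 0.9 × 0.30)/2.4 = 61.25%.
- OR for item 3.1 = (0.55/0.45)/(0.6125/0.3875) = 0.77. Reversing the two ratios gives 48.75% in controls and OR 1.28.
- Carried to item 3.1.1 at 10% prevalence, with untested counted as negative: 5.5% v 6.125%, OR 0.89.

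So a smaller distortion can remain after pooling when control ratios vary by site. SAP 7.3 is unconditional, and Appendix 1 lists the patient's location (item 1.4) but no participating-site variable.

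**The case against.** The strongest defence is the design. SAP section 4 draws controls from the same site and the same setting, so differences in laboratory policy and setting are largely balanced between cases and controls. This stands, and it makes the bias a possibility and not a certainty. What remains is variation within a site in who is tested, plus the pooling effect in step 4, which needs control ratios to be correlated with site testing rates.

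Second, the SAP may intend to use the panel. Section 7.1 names no source, section 6.2 calls its list partial, and other central results that define the case classes are also absent from Appendix 1. This too stands in part: absence from that table does not prove that central data will be ignored. However, sections 7.2 and 7.3 tie the analyses to Appendix 1, where 3.1 and 3.1.1 are the only laboratory entries for other pathogens. If linkage is intended, the SAP should say so.

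Third, item 3.1 implements protocol 3.2.6, which asks for evidence of other pathogens within 7 days either side of the sample. That window covers samples the panel never sees, and items 5.9 and 5.9.1 separately record alternative causes of diarrhoea. These are good reasons to keep the local items as description. They do not make them uniform measurements, since items 5.9 and 5.9.1 also come from the notes.

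A reader might infer from step 2 that the planned pathogen odds ratio will be wrong by the amounts shown there. The documents do not support this. Those values require untested patients to be coded as negative, which the SAP does not state.

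**Conclusion.** The point holds as a weakness in how a variable is defined. As written, the plan allows being tested to be selected and ranked as a CDI risk factor, and it supplies pathogen results only for locally tested patients, although a uniform measurement is planned on the same samples.

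The size and direction of any bias cannot be derived from the documents. For item 3.1, modest assumed differences in testing (50% v 60%) give an OR of 0.67. For pathogen results, the range is 0.61 to 1.36 under the assumed rates in step 2 with untested patients coded as negative, and 1.0 among tested patients if testing is unrelated to pathogen status. With equal testing there is no bias under either coding.

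It would go too far to infer that the SAP deliberately prefers the weaker source, or that its other comparisons, such as age, antibiotics or surgery, are biased. Nothing here shows either. The change is worth making because it is cheap and replaces a selectively recorded variable with a uniform one.

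**What to change.** In SAP 6.2, 7.1 to 7.3 and Appendix 1:

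- Define concomitant enteric pathogen from the central bioFire result on the index sample, as any target other than *C. difficile* and also by target. Merge it by study number for all cases and controls with a panel result, and report how many have none.
- Keep items 3.1 and 3.1.1 as descriptions of local practice over the 7 days either side of the sample, outside the risk-factor model.
- Code untested patients as not tested, never as negative.
- Optionally, add a sensitivity analysis limited to controls with no other pathogen on the panel.

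The cost is SAP wording and one merge of data already planned. No new testing or CRF work is needed.

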# 1.3 Study design of COMBACTE-CDI (overview)

To achieve our objectives, a large, complex study will be carried out (Figure 1), using proven methodology from a previous European wide (20 countries) CDI surveillance project (EUCLID network). In short, hospitals/laboratories of interest which carry out diagnostic testing of samples from both in-patients and community patients (including Long-Term Care Facilities patients) will be approached for inclusion. Hospitals/laboratories of interest will be selected to give respective coverage, based on population size, in the countries of interest and to represent North, South, East and West Europe.

Two study days will be selected, and all diarrhoeal stool samples received on those days by the hospital/laboratory in the study will be sent (regardless of age of patient or test requested) to the European Coordinating Laboratory (Leeds), where samples will be tested for CDI using the recommended 'optimal' testing methodology (ESCMID guidelines) (O1.1). Relevant ethical approvals will be sought (please see ethics section 1.4). Results will be compared to those from the submitting hospital/laboratory, including if the sample was even tested. Missed cases will be identified, enabling an estimation of the true burden of disease in both hospitals and the community. Isolates of *C. difficile* identified from the community and hospital samples will be sent for further analysis; including PCR-ribotyping, toxinotyping and whole genome sequencing to identify factors that may be driving clustering of strains (O1.2). Additional strains of animal and food origin collected from an existing network (NLZOH) will be added to the analysis for comparison between human and animal strains.

A clinical report form (CRF) will be designed to capture data for risk factor analysis and outcome data on all positive (ECL defined) and a proportion of CDI negative samples; completed 6 months after sample collection data (O 1.3 and 1.4). Please see section 1.4 for relevant ethical considerations.

All data collected from O1.1, 1.2, 1.3 and 1.4 will be brought into the analysis for transmission modelling in O1.5.

Hospitals/laboratories and their associated community practices will complete a surveillance questionnaire regarding:

- Testing policy and methodology;
- Surveillance practices;
- Guidelines available and compliance;
- The criteria for stratification of patients into 'severe' or 'non-severe' cases

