# Describe current treatment pathways for patients with CDI infection and recurrences (objective 2.4)

Current European treatment guidelines were published in 2014, but there are a paucity of data on national guidance and compliance with these guidelines. Guidelines often focus on in-patients and we will explore whether altered guidance is needed for different healthcare settings (see WP1). By building on networks used to establish variations in CDI diagnosis (EUCLID, LUCID, CLOSER), we will measure variability in treatment policies across Europe, focussing on the treatment/prevention of recurrent CDIs. By using the network of hospitals/laboratories established for the main study (O1.1.2), and their associated community practices, we will close the knowledge gaps within the community setting, with focus on long-term healthcare facilities. Comparisons will be made between healthcare locales/types and countries. Because information of outpatient costs of CDI are scarce, these new networks will also be used for further health-economic evaluations to analyse direct and indirect costs of patients with CDI outside hospitals (this data will feed in to O2.5 and 2.6).

Current guidelines on CDI treatment take into account both initial and recurrent episodes. For initial CDI treatment, pathways are mainly based on stratification on the severity of the disease; for recurrence, on the frequency of CDI episodes. The main concerns/knowledge gaps of these guidelines are represented by 1) heterogeneous definitions of severity  increasing rates of resistance to the often 1st-line treatment option metronidazole  lack of data on the risk of poorer outcomes in selected populations with CDI e.g. inflammatory bowel disease. Recently, Kanhafer *et al* demonstrated that the proportion of severe CDI cases varied widely (11-59%) depended on the definitions/risk factors used. This is important not only for stratifying patients for management strategies, including new treatments, but also for comparing data across studies. Some risk factors are also controversial; albumin levels could be the cause or effect of severe CDI. Studies should be addressed to better identify the role of these factors.

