This enriched case/control study will provide data on the difference in severity of CDI and the risks and outcomes for these different 'diagnostic types'. There are a paucity of data on these differences, particularly with regard to the new technology of the SIMOA assay. A retrospective CDI case-control study is proposed to determine the outcomes and risk factors for CDI, but different diagnostic criteria, for patients both within the hospital setting and in the community.

Ethical and regulatory approvals are in place for each site within the case/control study, as per the COMBACTE-CDI full study protocol.

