	CDI graded?			when the sample
				was taken
4.5.1	If yes, please record	Categorical	Univariate/multivariate	Patient admission
	the severity of CDI			when the sample
				was taken
4.6	Has the patient	Binary	Univariate	Patient admission
	ever had CDI			when the sample
E Clinica	Information			was taken
5.1	Temperature	Continuous	Univariate	Patient admission
5.1	(highest reading +/-	Continuous		when the sample
	3 days of the index			was taken
	sample)			
5.2	Serum creatinine	Continuous	Univariate	Patient admission
	(highest reading +/-			when the sample
	3 days of the index			was taken
	sample)			
5.3	White cell count	Continuous	Univariate	Patient admission

	(highest +/-3 days			when the sample
	of the index			was taken
	sample)			
5.4	Serum Albumin	Continuous	Univariate	Patient admission
	(lowest +/-3 days of			when the sample
	the index sample)			was taken
5.5	Primary diagnoses	Categorical	Univariate	Patient admission
	at time of index			when the sample
	sample			was taken
5.6	Does the patient	Binary	Univariate	Patient admission
	have any significant			when the sample
	illnesses			was taken
5.6.1	If yes, are the	Categorical	Univariate	Patient admission
	illnesses:			when the sample
				was taken
	Acute/chronic			
5.6.2	Please provide	Categorical	Univariate	Patient admission
	details of the			when the sample
	significant illness			was taken
5.7	Co-morbidities		All of these could be	
			Covariates	
	Myocardial	Binary	Univariate/multivariate	Patient admission
	infarction			when the sample
				was taken
	Congestive heart	Binary	Univariate/multivariate	Patient admission
	failure			when the sample
	De debe velo e e de c	D'		was taken
	Peripheral vascular	Binary	Univariate/multivariate	Patient admission
	uisease			when the sample
	Corobrovascular	Pipany	Univariato (multivariato	Rationt admission
	disease	Billary	Onivariate/multivariate	when the sample
	uiscase			was taken
	Dementia	Binary	Univariate/multivariate	Patient admission
	Dementia	Dinary		when the sample
				was taken
	COPD	Binary	Univariate/multivariate	Patient admission
		,	,	when the sample
				was taken
	Peptic Ulcer disease	Binary	Univariate/multivariate	Patient admission
				when the sample
				was taken
	Cystic fibrosis	Binary	Univariate/multivariate	Patient admission
				when the sample
				was taken
	Diabetes without	Binary	Univariate/multivariate	Patient admission
	organ damage			when the sample

			was taken
Leukaemia within	Binary	Univariate/multivariate	Patient admission

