	symptoms at time			was taken
	of index sample			
5.9	Was there an	Binary	Univariate	Patient admission
	alternative cause			when the sample
	for the patients			was taken
	diarrhoea			
5.9.1	If yes please give	Categorical	Univariate	Patient admission
	details			when the sample
				was taken
5.10	Duration of	Number of	Univariate	Patient admission
	diarrhoea before	days of		when the sample
	and after the index	diarrhoea is		was taken
F 44	sample	Continuous		Detionst e destade
5.11	Did the patient	віпагу	Univariate	Patient admission
	undergo any			when the sample
	diagnostic			was taken
	procedures for this			
	episode of CDI?			
5.11.1	It yes, please	Categorical	Univariate	Patient admission
	complete the table			when the sample

				was taken
5.12	Evidence of colitis	Binary	Univariate	Patient admission
				when the sample
				was taken
5.12.1	If yes please give	Categorical	Univariate	Patient admission
	details			when the sample
				was taken
5.13	Was the patient in	Binary	Univariate	Patient admission
	contact with a			when the sample
	diagnosed			was taken
	Clostridium difficile			
	case in the			
	preceding 3 months			
E 12 1		Catagorical	Univariato	Dationt admission
5.15.1	the date	Categorical	Univariate	when the sample
				was taken
5.14	Was the patient in	Binary	Univariate	Patient admission
	kissing contact of	Dinidi y	omratice	when the sample
	an infant in the			was taken
	preceding 3 months			
	to the sample?			
5.14.1	If yes please give	Categorical	Univariate	Patient admission
	the date			when the sample
				was taken
5.15	Did the patient	Binary	Univariate	Patient admission
	receive mechanical			when the sample
	ventilation			was taken
5.15.1	If yes, please give	Continuous	Univariate	Patient admission
	une duration of the			when the sample
	minutes			was taken
5.16	Was the patient	Binary	Univariate	Patient admission
	source isolated due			when the sample
	to CDI			was taken
5.16.1	If yes, please give	Continuous	Univariate	Patient admission
	the duration of			when the sample
	source isolation in			was taken
	days			
5.16.2	Did the patient in	Binary	Univariate	Patient admission
	source isolation			when the sample
	lead to the blocking			was taken
- 10 -	of beds			
5.16.3	If yes, how many	Continuous	Univariate	Patient admission
	beas were blocked			when the sample
6 Dave 11	uuring that time?			was taken
6. Drug H	istory			

6.1	Was the patient prescribed	Binary	Univariate/multivariate	Patient admission when the sample was taken

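### The recorded CDI severity grade (SAP Appendix 1, item 4.5.1) has no common scale and would normally be missing for controls and locally missed cases, so it should not be a regression covariate or a cross-group severity measure

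*SAP*

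**What the plan says.** **SAP, Appendix 1.** Item 4.5 ("Was the severity of" CDI graded, yes or no) is tagged univariate. Where the answer is yes, item 4.5.1 records "the severity of CDI" as a categorical variable tagged "Univariate/multivariate". Neither item names a scale, a set of criteria or who assigns the grade.

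Items 5.1-5.4 collect temperature, serum creatinine and white cell count (highest value) and "Serum Albumin" (lowest value), all within 3 days either side of the index sample. They are continuous and tagged univariate only, as is item 5.12, "Evidence of colitis". The SAP does not combine them into a grade.

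**SAP, main text.** The Introduction says: "This enriched case/control study will provide data on the difference in severity of CDI and the risks and outcomes" for the different diagnostic types. Section 2.5 adds comparison of outcomes between countries and between hospital and community. Section 7.2 compares continuous variables between cases and controls and looks at consistency across countries and settings. Section 7.3 describes the only regression: unconditional logistic, case/control status as the dependent variable, with every variable from the univariate analysis as a candidate.

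**Protocol.** Section 3.2.2 lists severity as a secondary outcome and illustrates it with white cell count, albumin and temperature. The rationale for Objective 2.4 calls severity definitions heterogeneous and cites a study in which "the proportion of severe CDI cases varied widely (11-59%) depended on the definitions/risk factors used". Section 1.3 includes in the site questionnaire: "The criteria for stratification of patients into" severe and non-severe. Section 5.0 says central results are not returned to the participating laboratories.

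**The concern.** The protocol treats severity grading as a practice that varies and that the study will describe. The SAP takes the resulting label and tags it as a patient variable for modelling. Two things can then go wrong.

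- **Meaning.** If sites grade by different rules, the same label describes different patients. A difference between countries, settings or diagnostic types may then be partly a difference in rules.
- **Availability.** A grade exists only where someone graded an episode as CDI. Whether that happened depends on local recognition, which may differ between diagnostic types, and that is the contrast the SAP sets out to describe. It also depends on being a case at all, which is the outcome of the only regression.

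Severity is a protocol secondary outcome and the first difference the SAP promises, so the choice of variable affects a reported result.

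**Working it through.** **1. Tags.** Among items that record CDI severity itself, only 4.5.1 carries the multivariable tag; 5.1-5.4 and 5.12 do not. Treatment escalation (7.1, 7.2) and CDI-linked death (10.5.1, 10.7.1) also carry it, but protocol 3.2.2 lists escalation and mortality separately from severity.

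**2. Tags against SAP 7.3.** Section 7.3 admits every variable in the univariate analysis. Read literally, 5.1-5.4 enter the model too. The Appendix tags and 7.3 cannot both be followed.

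**3. Who would have a grade.** Table 1 gives 103 + 71 + 39 = 213 cases and 512 controls (213 + 512 = 725).

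- Controls are negative by all assays, and SAP 4.1.5 removes those with a CDI-positive sample within 8 weeks of the index sample. A CDI grade would not normally exist for them.
- Cases missed locally would not normally be graded either, because central results are not returned. Of the cases, 71 + 39 = 110 of 213 are CCNA-negative. The documents do not say how many of these were recognised locally.

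If 4.5.1 is entered in a case/control model, dropping ungraded records removes nearly all controls. Coding them as not graded creates a category that largely restates control status. Neither gives an interpretable coefficient.

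**4. How far definitions alone could move a comparison.** The 11% and 59% come from a study cited in the protocol and cannot be reproduced from the documents. Taken as given, the worst case is one group graded entirely by the widest rule and the other entirely by the narrowest:

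- difference: 59% − 11% = 48 points
- odds ratio: (0.59/0.41) / (0.11/0.89) = 11.6

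For milder imbalance, assume equal true severity in both settings and that each case is graded by either the 59% or the 11% rule. The expected severe share in a setting is 0.11 + 0.48 × (share graded by the wide rule). The chance of p<0.05 is the usual normal approximation for two proportions (two-sided 5%), with the 57 community cases at the higher share and the 156 hospital cases at the lower. Reversing the direction lowers the chances slightly (for example 91% and 35% in place of 92% and 39%).

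| Wide-rule share in the two settings | Severe share | Odds ratio | Chance of p<0.05, all graded | Half graded |
|---|---|---|---|---|
| equal | 35% v 35% | 1.0 | no bias | no bias |
| 62.5% v 37.5% | 41% v 29% | 1.7 | 39% | 22% |
| 75% v 25% | 47% v 23% | 3.0 | 92% | 66% |
| 100% v 0% | 59% v 11% | 11.6 | about 100% | about 100% |

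The mix of rules across sites is not in the documents, so these rows are assumptions that show a range. They are not estimates of the bias in this study.

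**5. What is not affected.** Items 5.1-5.4 have one collection rule for everyone and do not pass through a local grade. Their univariate comparisons under 7.2 stand.

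**The case against.** The strongest case against is that the protocol's severity outcome never rested on item 4.5.1. Protocol 3.2.2 illustrates it with measured markers, the SAP collects those markers under uniform rules, and 7.2 compares them. This stands. A reader might infer that all severity findings will reflect local definitions, and the documents do not support that.

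Second, the only regression has case/control status as its outcome, so no planned model compares grade across sites or countries. This also stands. A reader might take 11.6 as a result the analysis would produce; it is a bound for an extreme contrast that no specified model estimates. The same fact counts against the tag, because 4.5.1 has no usable role in that regression.

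Third, the documents do not say that grading is local. It is a fair inference from an item asking whether severity was graded, but protocol 3.2.6 mentions a procedure supporting the CRF that is not available here and might set a common rule. The protocol also attributes the 11-59% range to definitions and risk factors together, so it should not be read as the effect of definition alone.

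Fourth, a central grade imposes one definition where the protocol says the choice matters and that albumin may be a cause or an effect of severe disease. Analysing the markers separately is legitimate. That argues for reporting the markers alongside any derived variable, and for deriving it among cases only, not for the 512 controls.

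**Conclusion.** The point holds in a limited form. Item 4.5.1 has no stated scale, exists only where a grade was assigned, and is tagged for multivariable analysis. It cannot work as a covariate in the case/control regression. Used to compare severity between diagnostic types, countries or settings, it could mix patient severity with local definitions and local recognition of CDI.

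The size of that bias is unknown. It ranges from none from definitions, if they are spread equally across the groups, to a worst-case odds ratio of 11.6. With 156 hospital and 57 community cases, moderate imbalance could produce a nominally significant difference. The conclusion assumes that grading was done locally without a common rule and that controls and locally missed cases were generally not graded. If the CRF procedure fixes a common rule, the definition problem falls away, but the covariate problem remains. The marker comparisons are sound as planned.

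**What to change.** - Remove item 4.5.1 from the case/control regression and from severity comparisons. Keep it for describing local stratification practice in work package 2, alongside the site questionnaire.
- Base severity comparisons among cases on items 5.1-5.4, in line with protocol 3.2.2. Report the markers themselves and one severity variable derived centrally by a single definition that the sponsor fixes before analysis. Show patients without results as a separate category, by diagnostic type and setting.
- State which reading is used: protocol 3.2.6 refers to the nearest value for temperature, creatinine and white cell count, while Appendix 1 takes the highest. The two need reconciling.
- Reconcile the Appendix 1 tags with SAP 7.3, so that it is clear which variables may enter the model.

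The cost is SAP wording and one derived variable from data already collected. The drawback is that patients without blood results get no central grade. They may be more common in the community, which limits the hospital/community comparison and should be reported with it.
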